## **Psychosocial Rehabilitation after Moral Injury and Loss with Adaptive Disclosure**

### **OBJECTIVES**

The overarching goal of this study is to conduct a multi-site randomized control trial comparing Adaptive Disclosure-Moral Injury and Loss (AD-MIL), a new combat-specific psychotherapy for PTSD stemming from military trauma, to Present Centered Therapy (PCT; Frost et al., 2014), in terms of its impact on psychosocial functioning. We have seven hypotheses, grouped into (A) functional change and (B) mental health change.

#### **A: Functional and behavioral change hypotheses:**

- A.1.** Immediately post-treatment, 3-, and 6-months post-treatment, veterans with PTSD randomized to AD-MIL will have greater reductions in social, educational, and occupational disability
- A.2.** COVID-19 aim. In the extended time period for the trial, at the post-treatment, or post-treatment and 3-months post-treatment intervals (depending on when the participant was randomized), veterans with PTSD randomized to AD-MIL will have greater reductions in social, educational and occupational disability

#### **B: Mental health change hypotheses:**

- B.4.** Veterans randomized to AD-MIL will have greater reductions in PTSD symptom severity and a smaller percentage of PTSD cases
- B.5.** Veterans randomized to AD-MIL will have greater reductions in depressive symptoms
- B.6.** Veterans randomized to AD-MIL will have greater reductions in shame and guilt
- B.7.** Veterans randomized to AD-MIL will have greater reductions in psychological distress

We will also explore the impact of treatment on anger and aggressive behaviors, suicidal ideation, alcohol abuse, compassion towards self and others, and social connectedness.

### **BACKGROUND**

Posttraumatic stress disorder (PTSD) is a highly prevalent and disabling condition among military veterans, posing a significant public health burden. Depending on the degree and type of exposure to military stressors, approximately 20% of the 2.5 million service members who served in Iraq and Afghanistan have or will develop clinically significant PTSD (Hoge et al., 2004; Milliken et al., 2007; [name] & Schlenger, 2009). PTSD causes private suffering and has a uniquely damaging ripple effect on family members, friends, co-workers, productivity, and healthcare costs. Veterans with PTSD suffer from a variety of co-morbid mental and physical health conditions (Buckley et al., 2004; Kulka et al., 1990) and are heavy service-utilizers (e.g., Calhoun et al., 2002). They also have extensive functional impairments, such as occupational problems (Hoge et al., 2005; Savoca & Rosenheck, 2000), family and relationship difficulties (e.g. Riggs et al., 1998), aggressive and risky behaviors (e.g. McFall et al., 1999), and reduced quality of life (e.g., Buckley et al., 2004). Unfortunately, although considerable gains have been made in the VA's dissemination of PTSD treatments that are highly effective with civilian trauma, these therapies have been shown to work considerably less well for war trauma (Steenkamp & [name], 2013). We have argued that this is partly due to a lack of attention to the military culture and ethos and the heterogeneous harms of war trauma, including life threat, moral injury (MI) and traumatic loss (TL). In addition, VA treatments have failed to demonstrate an impact on functioning and quality of life, problems that are no less impacted by the military trauma being targeted in treatment. Instead, symptom change is typically the sole metric of success, and functional deficits are rarely taken into account. We argue that PTSD symptoms should be conceptualized and targeted as part of the fabric of the whole veteran and his or her context. Consequently, the overarching goal of this proposed study is to fill a substantial care-gap in the VA by

creating an evidence-based treatment for military-related PTSD focusing on improving psychosocial functioning. We have modified and extended Adaptive Disclosure (AD; [name] et al., 2015) by building in skills training and behavioral contracting to improve functioning and reducing behavioral obstacles to positive and potentially habitative engagements in occupational, relationship, and family roles. If found to be effective, AD-MIL will fill a care-gap in the VA, reduce PTSD patients' suffering, and help veterans reclaim or establish positive relationships, work roles, and self-care routines.

## METHOD

### Overview

We plan to conduct a multi-site randomized controlled trial of AD-MIL, comparing it to PCT (Frost et al., 2014). Study recruitment and treatment will occur off-site at four VA partnering sites: Minneapolis, MN, San Diego, CA (Oceanside CBOC), San Francisco, CA, and Waco, TX (Center for Returning Veterans Center of Excellence at the Central Texas Veterans Healthcare System; CTVHCS). VA Boston's research roles are to: (1) conduct weekly and PRN oversight and supervision meetings to problem-solve recruitment, treatment delivery, patient compliance, and data collection issues; (2) conduct blinded phone interviews to diagnose PTSD using the Clinician-Administered PTSD Scale for DSM-5 (CAPS-5) before treatment and at three time points after treatment; (3) manage and analyze de-identified data sets; and (4) help prepare manuscripts and reports.

The trial will follow the consensus recommendations for clinical trials in the VA (VA-ORD, 2008): (1) clearly defined target symptoms: Functional and clinical outcomes will be operationalized; (2) reliable and valid measures: Assessment tools are selected for their content relevance and psychometric properties; (3) use of blind evaluators of outcome: The evaluator will be independent and blind to treatment condition. The assessor will remind participants to help maintain their blind; (4) assessor training: The independent evaluator (IE) will be carefully trained to criteria and monitored on an ongoing basis; (5) manualized, replicable, specific treatment programs; (6) unbiased assignment to treatment arms and (7) treatment adherence: Sessions will be recorded, and a random percentage will be used to assess treatment integrity. Adherence to the therapy manuals will be monitored by senior supervisors. We will follow the CONSORT guidelines for randomization and participant tracking.

### Participants

Participants will comprise a sample of 148 veterans (including women and members of diverse ethnic and racial groups) with PTSD as a result of military trauma.

To power the COVID-19 aim, we require 74 veterans (including women and members of diverse ethnic and racial groups) with PTSD as a result of military trauma.

#### *Inclusionary Criteria:*

1. Age 18 or older
2. Served in an active-duty role within the military since September 2001 (Veterans may be eligible whether or not they were deployed to a warzone)
3. Meet the DSM-5 diagnostic criteria for PTSD as a result of military trauma (per Clinician Administered PTSD Scale for DSM-5 [CAPS-5]) and report non-negligible levels of associated functional impairment (Sheehan Disability Scale [SDS] score  $\geq 10$ )
4. Prospective enrollees must be willing to commit to 12 consecutive weekly therapy sessions lasting up to 90 minutes in duration and to complete assessment materials.

#### *Exclusionary Criteria:*

1. Bipolar or psychotic disorders

- 2. Current drug or alcohol dependence (other than caffeine or tobacco dependence). Prospective enrollees who have maintained sobriety for at least 6 weeks immediately prior to the time of enrollment may be eligible.
- 3. Evidence of traumatic brain injury severe enough to influence the ability to understand and respond to study procedures
- 4. Suicidal or homicidal ideation severe enough to warrant immediate attention
- 5. Concurrent enrollment in any treatment that involves: (1) systematic disclosure of troubling trauma-related memories or (2) present-focused psychosocial skills training for PTSD or (3) supportive therapy/case management on a > monthly basis or (4) any individual therapy or (5) newly (< 6 weeks) prescribed pharmacological treatment.

### *Sample Size*

Power calculations were based on a two-sided, two-sample t-test to compare the differences in mean change. Effect sizes were selected based on a trial comparing Acceptance and Commitment Therapy with PCT in veterans with mental health diagnoses, using the SDS (Lang et al., 2016), which showed a large effect size for reduction in disability ( $d \approx .60$ ), a change of 1.2 points. Lang et al.'s (2016) follow-up interval was 3 months. These correspond to 3-month changes of 1.2 points assuming a standard deviation for the change of 2.1 points as per Lang and colleagues. These power calculations inflate the variance to account for clustering of scores (sites by therapists), with an  $ICC = .02$ . To partially offset possible losses to follow-up, we will follow the Benjamini-Hochberg testing procedure, which is less conservative than the Bonferroni rule (Benjamini & Hochberg, 1995). Each hypothesis is powered to compare outcome at 3 months. Analyses up to 6-months post-treatment are exploratory. Testing five hypotheses, each with Type I error of  $1\% = 5\%/5$ , then with 93 participants per arm, a two-sample t-test, comparing the difference between the 3-month changes, has 90% power to detect an absolute difference of .50 or larger assuming an effect size of .56. To have 80% power with 93 participants per arm requires an effect size of .50.

Note: In consultation with RR&D, we recalculated the number of participants to power the original trial at .8 (vs. .9) and this resulted in a new target N of 148 (74 per arm).

**COVID-19 Aim:** We used the AD grant's power framework to estimate the N required to test our hypothesis that AD would lead to better functional changes relative to PCT in COVID-19 stressed veterans with PTSD. We used the same parameters for mean change and the SD for change in Sheehan scores from the grant and a revised differential effect size prediction of .8. We reasoned that we would expect a larger differential effect size for this sub-study because AD can not only help veterans whose existing PTSD symptoms and impairments are exacerbated by COVID-19 stressors but also because AD includes change agents that can help reduce distress and impairment associated with the day to day demands and stressors of living in the time of COVID-19 (mindfulness, loving kindness meditation, letter-writing, behavioral assignments). With these parameters, we need 74 veterans (37 per arm) to power the aim (at a power of 0.90; one-tailed).

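### The Sample Size section gives a .50 difference that does not fit its own inputs, and claims a clustering inflation that is not visible in 93 or 74 per arm

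*Combined protocol and SAP*

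**What the plan says.** All of this is in the Sample Size section unless noted.

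- The test is a two-sided two-sample t-test on mean change, with five hypotheses at 1% each, powered at 3 months.
- The planning effect comes from an earlier trial of Acceptance and Commitment Therapy against PCT, "which showed a large effect size for reduction in disability" (d about .60, a change of 1.2 points), and the section continues "assuming a standard deviation for the change of 2.1 points as per" that trial.
- On clustering: "These power calculations inflate the variance to account for clustering of scores (sites by therapists", with ICC .02. No number of patients per therapist, design effect or pre-inflation SD is given.
- On loss to follow-up: "To partially offset possible losses to follow-up, we will follow the Benjamini-Hochberg testing procedure". No loss rate is given and N is not increased for loss.
- On detectable effects: with 93 per arm the t-test "has 90% power to detect an absolute difference of .50 or larger assuming an effect size of .56". The next sentence reads "To have 80% power with 93 participants per arm requires an effect size of .50".
- A note then lowers the power from .9 to .8, and "this resulted in a new target N of 148 (74 per arm". The Participants section agrees: "Participants will comprise a sample of 148 veterans". The detectable effects are not restated for 74 per arm.

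**The concern.** Two statements cannot be squared with the printed inputs. A difference of .50 is tied to an effect size of .56 and 90% power, yet the plan's difference is 1.2 points with SD 2.1, and the following sentence gives .50 a power of 80% at the same sample size. Separately, the text says the variance was inflated for clustering, but the sample sizes look like those of a plain t-test.

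The clustering point matters because therapists deliver one arm only (Treatment Training, Supervision, and Fidelity Monitoring), so variation between therapists adds directly to the variance of the arm comparison. At stake is how the SDS result will be read. A null finding would be judged against 80% power, and as written a reader cannot tell whether that figure allows for clustering or how much of it survives loss to follow-up. Someone who applies the printed .50 to the current 74 per arm would be misled about what the trial can detect.

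**Working it through.** **Inputs from the Sample Size section.** Difference 1.2; SD of change 2.1; two-sided alpha .01; equal arms; ICC .02. Effect size d = 1.2/2.1 = .571.

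**Formula.** Power is the probability that a noncentral t with 2n − 2 degrees of freedom and noncentrality d√(n/2) exceeds the two-sided 1% critical value in absolute value.

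**Step 1: reproduce the plan's sizes (design effect 1, no loss).**

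| n per arm | Power at d = .571 |
|---|---|
| 73 | 79.9% |
| 74 | 80.5% |
| 92 | 89.7% |
| 93 | 90.1% |

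Both published sizes are the exact minimum for an unclustered t-test with everyone followed up. Nothing is added beyond what SD 2.1 may already contain.

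**Step 2: could the inflation be inside SD 2.1?** Taking d = .60 as exact, the SD is 1.2/.60 = 2.0. Then (2.1/2.0)² = 1.1025, and 1 + (m − 1) × .02 = 1.1025 gives m = 6.1 patients per therapist. That is plausible, but the text presents 2.1 as the cited trial's SD, and .571 also rounds to .6.

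**Step 3: could .56 be the clustering-adjusted effect?** From .60, (.60/.56)² = 1.148, or m about 8.4. From .571, (.571/.56)² = 1.041, or m about 3. However, d = .56 gives 88.7% at 93 per arm and 78.6% at 74, and would need 97 and 77 per arm. That is close to the printed figures, but only d = .571 reproduces them exactly.

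**Step 4: the .50 difference at 93 per arm.**

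- As SDS points: .50/2.1 gives d = .24, with power 17%.
- As an effect size: power 79%, which matches the next sentence's 80% and not 90%.
- The stated d = .56 corresponds to .56 × 2.1 = 1.18 points.

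**Step 5: what 74 per arm detects.** For 80% power at two-sided 1% with full follow-up, d = .568, and .568 × 2.1 = 1.19 points. At 74 per arm the printed .56 and .50 have 79% and 67% power.

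**Step 6: if SD 2.1 is uninflated.** Patients per therapist (m) are not in the documents, so these are assumptions; 18.5 = 74/4 would be one therapist per arm at each of the four sites. The effect becomes .571/√(design effect), with 74 per arm, 1% level and full follow-up.

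| m | Design effect 1 + (m − 1) × .02 | Power |
|---|---|---|
| 5 | 1.08 | 77% |
| 10 | 1.18 | 72% |
| 18.5 | 1.35 | 65% |

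**Step 7: loss to follow-up.** Loss rates are also assumed. With d = .571, no added clustering and a completers' t-test at the fixed 1% level, 10% loss (66.6 per arm) gives 75% and 20% loss (59.2 per arm) gives 69%.

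**Step 8: Benjamini-Hochberg.** With five hypotheses, the threshold is 1% if one rejects, 2% if two do, and up to 5% if all five do. Simulated SDS power at 74 randomised per arm, with no added clustering, d = .571 for each real effect and assumed correlations of 0 to .5 between the test statistics:

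| Real effects | 10% loss | 20% loss |
|---|---|---|
| All five | about 88–90% | about 84–86% |
| SDS and one other | about 81% | about 75–76% |
| SDS only | about 76% | about 69–70% |

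**The case against.** The best defence has four parts.

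- **Testing is not at a fixed 1%.** Under Benjamini-Hochberg, 1% is the lowest threshold that applies. If all five effects are as large as planned, SDS power stays above 80% even with 20% loss. This stands, and it is why the 1%-level figures are floors. A reader might infer that 80% power is out of reach unless follow-up is complete and there is no further clustering. The documents do not support that, because the planned procedure can exceed 80% when other hypotheses also reject.
- **The text promises only a partial offset for loss.** This also stands. The section does not claim that Benjamini-Hochberg guarantees recovery, and the absence of a loss rate is a gap in reporting, not an arithmetic error.
- **Clustering may already be in SD 2.1, or in the .56.** Either is possible (steps 2 and 3). A reader might infer that the ICC adjustment was forgotten, but the documents do not establish that. What stands is that the text claims an inflation, attributes the SD to another trial, and shows no figure in which the inflation can be seen.
- **The analysis is a mixed model using all available data, and early terminators are still assessed** (Analyses; Follow-Up Assessments). So the completers' loss figures are probably pessimistic. This stands as a caution on step 7. It does not touch the .50 error or the clustering question.

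**Conclusion.** Two things are wrong as written. The .50 difference contradicts the plan's own inputs whether read as SDS points or as an effect size; this needs no assumption beyond the printed figures. The claimed ICC .02 inflation adds nothing visible to 93 or 74 per arm beyond what SD 2.1 may hold, and the text does not say that SD 2.1 holds it.

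The consequence for power is conditional. If SD 2.1 already contains the inflation, 74 per arm has 80.5% at the 1% level with full follow-up. If it does not, the figure falls to between 77% and 65% over the assumed 5 to 18.5 patients per therapist. Loss of 10% or 20%, without added clustering, gives about 75% or 69% at the same level. Benjamini-Hochberg may lift these, by an amount that depends on how many other effects are real. It would therefore go too far to call the trial underpowered; the supported conclusion is that the stated power cannot be interpreted until the clustering basis and the 1% condition are written down.

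**What to change.** Keep N = 148, the test and the endpoint, and revise the Sample Size section as follows.

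1. Replace .50 with the difference intended: 1.18 SDS points if d = .56 is meant.
2. Give the detectable difference for the current 74 per arm: d = .568, or 1.19 points, for 80% power at two-sided 1%, with full follow-up and no clustering beyond any already in SD 2.1.
3. Either show that SD 2.1 already includes the ICC .02 inflation (the SD before inflation, patients per therapist and the design effect), or restate the power at 74 per arm with the design effect applied. In both cases include the expected loss. The figures should come from the sponsor's own inputs; those above are illustrations.
4. Name the 1% level as the condition on the stated power, and report any Benjamini-Hochberg gain separately, as conditional on other hypotheses rejecting.

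The cost is rewording one section. No extra patients are needed. The downside is that the stated power may become less favourable.

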**Hypotheses 3-6:** Veterans in AD-E will have: (3) steeper downward PTSD symptom severity slopes (CAPS-5 and PCL-5) and lower incidence of PTSD cases (tested with Chi-square); (4) steeper slopes in depressive symptoms (PHQ-9); and (5) steeper slopes in shame and guilt (TRSI and TRGI); (6) steeper slopes in overall psychological distress (SOS) Separate models will be tested for each outcome. These models will be structured the same as the model used to test Hypotheses 1 and 2, with the above continuous measure scores designated as the outcome variables in separate analyses.

**Exploratory analyses:** Will AD-E be associated with steeper downward slopes in anger and aggressive behaviors (DAR-5, CTS2), suicidal ideation (DSI-SS), and alcohol abuse (QDS) as compared to PCT? Will AD-E be associated with steeper upward slopes in compassion towards self (SCS), compassion towards others (SBCS), and social connectedness (SoCS) as compared to PCT? The models used to evaluate these questions will be structured the same as the models above. We will be especially circumspect about statistically significant findings for these variables.

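### The statement that each hypothesis is powered rests on one SDS t-test calculation, which does not cover the chi-square comparison of PTSD cases in hypothesis B.4

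*Combined protocol and SAP*

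**What the plan says.** The Sample Size section (Method, Participants) describes one calculation: "Power calculations were based on a two-sided, two-sample t-test to compare the differences in mean change". Its effect size comes from one earlier trial of another therapy against PCT, "using the SDS (Lang et al., 2016), which showed a large effect size for reduction in disability". The inputs are then given in SDS units: "These correspond to 3-month changes of 1.2 points assuming a standard deviation for the change of 2.1 points". The alpha is set per hypothesis, "Testing five hypotheses, each with Type I error of" 1% (5%/5), while the same paragraph also says "we will follow the Benjamini-Hochberg testing procedure, which is less conservative than the Bonferroni rule". It then generalises: "Each hypothesis is powered to compare outcome at 3 months". A note below it moves the target to 74 per arm at 80% power.

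Hypothesis B.4 in the Objectives has two parts: "Veterans randomized to AD-MIL will have greater reductions in PTSD symptom severity and a smaller percentage of PTSD cases". In the ANALYSES section, where the same hypothesis is numbered 3, the second part becomes "lower incidence of PTSD cases (tested with Chi-square".

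No follow-up case rate is given for either arm. No outcome-specific effect size or SD is given for CAPS-5, PCL-5, PHQ-9, TRSI, TRGI or SOS-10.

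**The concern.** A power figure belongs to a particular test of a particular outcome. A t-test on a continuous change score does not give the power of a comparison of two percentages, and splitting a continuous severity measure into case and non-case usually loses information. The blanket sentence therefore attributes to the case comparison a property that has not been calculated for it.

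What is at stake is interpretation. If caseness does not differ between the arms, a reader who relies on the sentence would take this as a negative result from a test with 80% power. The chance of missing the planned effect may in fact be much larger.

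**Working it through.** **Inputs from the Sample Size section.** 74 per arm (93 before the revision); alpha .01 two-sided; d = .56 as stated, or 1.2/2.1 = .571. **Assumed, because the documents give no figure:** PCT case rate at 3 months of 40-80%, full follow-up, no clustering.

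**Step 1. Reproduce the plan's figures.** Normal approximation: power = Φ(d√(n/2) − 2.576).
- n = 93, d = .56: Φ(3.819 − 2.576) = 89.3% (noncentral t 88.7%); stated 90%.
- n = 93, d = .50: Φ(3.410 − 2.576) = 79.8% (t 78.9%); stated 80%.
- n = 74, d = .56: 79.7% (t 78.6%); d = .571: 81.6% (t 80.5%); stated 80%.

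The figures reproduce within 2 points, but only with no clustering inflation. The section says an ICC of .02 was applied and gives no cluster size. With design effect 1 + (m − 1) × .02, clusters of m = 5 give 74/1.08 = 68.5 effective per arm and about 75% power at d = .56. Clusters of m = 10 give 74/1.18 = 62.7 and about 70%.

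**Step 2. Carry the planning effect over to case status.** Chi-square power = Φ{[|p₁ − p₂| − 2.576√(2p̄(1 − p̄)/n)] / √[(p₁(1 − p₁) + p₂(1 − p₂))/n]}, with p₁ the PCT rate, p₂ the AD-MIL rate and p̄ their mean.

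*Normal threshold model:* p₂ = Φ(Φ⁻¹(p₁) − d). For p₁ = .60 and d = .56, p₂ = .380. The numerator is .2204 − 2.576 × .0822 = .0087, the denominator is .0802, and power is about 54%.

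| PCT case rate | 40% | 50% | 60% | 70% | 80% |
|---|---|---|---|---|---|
| Power, d = .56 | 48.5% | 52.7% | 54.4% | 53.1% | 47.9% |
| Power, d = .571 | 50.4% | 54.8% | 56.5% | 55.3% | 50.0% |

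At a PCT rate of 30% power is about 42-43%, and at 90% about 35-37%.

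*Logistic conversion:* OR = exp(πd/√3) = 2.76 at d = .56. Power is about 57-68% across PCT rates of 40-80%.

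*Change-score effect to end-point status:* the plan's d is divided by the SD of change, but case status is read at a single time point. With equal SDs at both times and baseline/follow-up correlation r, the end-point effect is d√(2(1 − r)). The threshold model above therefore implies r = .5. With d = .571:
- r = .3: .571 × 1.183 = .676, power 67-75%.
- r = .7: .571 × .775 = .443, power 27-33%.

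**Step 3. Relax alpha.** With five hypotheses, the Benjamini-Hochberg rejection level for one of them runs from .01 to .05. At .05 the threshold model gives about 72-77% (d = .56) and 74-79% (d = .571), and the logistic conversion at d = .56 gives about 79-86%.

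**Step 4. Detectable difference.** Solving the chi-square formula for 80% power at n = 74 and alpha .01 gives differences of 24.9, 26.8, 27.7, 27.6 and 26.2 percentage points at PCT rates of 40, 50, 60, 70 and 80%. This step does not use d or any conversion.

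**The case against.** Four points can fairly be made for the plan.

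1. **The shortfall has no single value.** A reader might infer that the plan's own effect fixes caseness power at 50-57%. It does not. That band needs an assumed case rate, a cut on a normal score, d = .571 rather than the stated .56, and an unstated correlation of .5. The Measures section also defines a case by ratings on the DSM-5 criteria, not by a cut on total severity. This stands, so only ranges are given here.

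2. **The plan names Benjamini-Hochberg.** The 1% level is its strictest step, and at .05 some conversions pass 80%. This stands as a qualification. However, the plan's own power statement uses 1%, so 1% is the like-for-like comparison.

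3. **A standardised effect can serve several outcomes.** A reader might infer that CAPS-5, PCL-5, PHQ-9, TRSI, TRGI and SOS-10 are not covered at all. They are covered conditionally: if the same d holds for them, so does the t-test calculation. What is missing is a statement of, and reason for, that condition.

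4. **B.4 is more than caseness.** A reader might infer that B.4 fails unless both severity and caseness succeed. Neither the Objectives nor the analysis section says so. The shortfall concerns the caseness part only.

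The objection does not supply a power calculation for the chi-square test, and the blanket sentence still includes it.

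**Conclusion.** The point holds in a limited form. The plan claims power for each hypothesis but shows it only for a t-test on mean change with SDS inputs. That much can be read from the text without any assumption.

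The size of the gap does depend on assumptions. For PCT case rates of 40-80%, at 74 per arm and 1% alpha with full follow-up and no clustering, caseness power is below 80% under every conversion tried: about 48-57%, 57-68% or 27-75%, depending on the conversion. Dropout or clustering would lower these figures. At the .05 step, a shortfall on every conversion cannot be claimed.

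The clustering check might tempt a reader to conclude that the SDS comparison itself is underpowered. The documents do not settle this. The stated 80% reproduces only without the inflation that the plan says it applied, but no cluster size is given, so the figure needs reconciling before it is repeated.

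**What to change.** In the Sample Size section, replace the blanket sentence with a statement that:
- limits the power calculation to the SDS comparison of mean change at 3 months;
- says the other continuous outcomes have that power only if the same standardised effect holds for them;
- says the PTSD-case comparison is not separately powered, and that at 1% alpha with 74 per arm, 80% power needs a difference of about 25-28 percentage points for assumed PCT case rates of 40-80%, with full follow-up and no clustering.

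Do not restate 80% for the SDS until it has been reconciled with the ICC = .02 inflation, including the cluster size used.

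The change is to wording only and N stays the same. The cost is a less favourable stated power for caseness. Naming CAPS-5 severity as the single test of B.4 is a design choice open to the sponsor and is not part of this correction.
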